5.4 Randomization

Randomization is not an option in this investigation. All subjects will utilize both the ds-MCE and the EGD during the study.

5.5 Blinding

- (1) The ds-MCE operator will be aware of the subject's medical history and blinded to the EGV-related imaging and endoscopic findings of the enrolled subjects;
- (2) The EGD operator will be aware of the subject's medical history, but will be blinded to the ds-MCE examination results;
- (3) The independent ds-MCE imaging readers will be blinded to the EGD assessment results of the enrolled subjects;
- (4) The independent EGD readers will be blinded to the ds-MCE assessment results of the enrolled subjects.

6. Efficacy and Safety outcomes

6.1 Efficacy outcomes

6.1.1 Primary Outcome

The primary outcome is the sensitivity and specificity of ds-MCE to identify EGV in patients with cirrhosis, using detection by EGD as the reference.

6.1.2 Secondary Outcomes

6.1.2.1 Key Secondary Outcome

- 1) The sensitivity, specificity of ds-MCE in detection of high-risk EV, using the detection by EGD as the reference.

The high-risk EV was identified by either large EV or small EV with presence of red signs according to the Baveno VI consensus².

6.1.2.2 Other Secondary Outcomes

- 2) The sensitivity, specificity, positive predictive value (PPV), negative predictive value (NPV) and overall diagnostic accuracy of ds-MCE in detection of high-risk EGV, using the detection by EGD as the reference.
High-risk EGV are defined as high-risk EV or any GV^{3,4}.
- 3) The sensitivity, specificity, PPV, NPV and overall diagnostic accuracy of ds-MCE in detection of EV, using the detection by EGD as the reference.
- 4) To investigate the optimal threshold of the proportion of ds-MCE esophageal luminal circumference occupied by the largest EV present in differentiating large

EV from small or no EV, using the detection by EGD as the reference.

- a) EV identified during EGD are classified based on the standard Baveno III consensus to differentiate between large EV (varix diameter ≥ 5 mm) and small EV (varix diameter < 5 mm)⁵.
- b) As grading EV by endoscopy requires fully distention of the esophagus with air insufflation, which is lacking in CE, there has been no consensus on the standard classification of large EV under ds-MCE. In this study, we grade the EV under ds-MCE according to the proportion of the esophageal luminal circumference occupied by the largest EV present⁶.
- c) The Youden Index, defined as $[(\text{sensitivity} + \text{specificity}) - 1]$, will be calculated to determine the optimal ds-MCE luminal circumference percentage threshold derived from the training cohort that resulted in the best combination of specificity and sensitivity for distinguishing large EV, using the results of EGD as the reference standard.

5) The sensitivity, specificity, PPV, NPV and overall diagnostic accuracy of ds-MCE in detection of large EV, using the detection by EGD as the reference.

- a) EV under EGD are classified into three grades: no, small or large, with the latter signifying a diameter ≥ 5 mm.
- b) EV under ds-MCE are classified into three grades: no, small or large, with the latter signifying that the esophageal varix occupied more than the prespecified “optimal threshold” proportion of the esophageal luminal circumference.

6) The sensitivity, specificity, PPV, NPV and overall diagnostic accuracy of ds-MCE in detection of the red sign of EV, using the detection by EGD as the reference.

7) The sensitivity, specificity, PPV, NPV and overall diagnostic accuracy of ds-MCE in detection of gastric varices (GV), using the detection by EGD as the reference. GV are classified according to Sarin’s classification⁷. GV could be classified on the basis of its location in the stomach and its relationship with EV during ds-MCE procedure and EGD procedure. These are divided into two groups: gastroesophageal varices (GOV) and isolated gastric varices (IGV). GOV1 are the extension of esophageal varices which across the cardia onto the lesser curve, and GOV2 extend onto the fundus. Isolated gastric varices (IGV) are vascular protrusions without direct connection to the esophageal varices. IGV1 are located in the fundus, while IGV2 are located elsewhere in the stomach, typically in the

distal body and antrum.

8) The sensitivity, specificity, PPV, NPV and overall diagnostic accuracy of ds-MCE in detection of cardiofundal GV, using the detection by EGD as the reference. Cardiofundal gastric varices including GOV2 and IGV1 are at high risk of bleeding due to the unique vascular anatomy as opposed to lesser-curvature gastric varices (GOV1)⁸.

9) The sensitivity, specificity, PPV, NPV and overall diagnostic accuracy of ds-MCE in detection of portal hypertensive gastropathy (PHG), using the detection by EGD as the reference. The PHG is classified as four elementary gastric endoscopic signs proposed by the NIEC group: mosaic like pattern (MLP); red point lesions (RPL); cherry red spots (CRS); black brown spots (BBS)^{9,10}.

10) The incidence of PHE in small bowel under ds-MCE. Endoscopic findings of PHE include mucosal inflammatory-like abnormalities, vascular lesions and spontaneous bleeding induced by mucosal inflammatory-like abnormalities or vascular lesions¹¹⁻¹³.

11) Examination time of ds-MCE and EGD procedures. Examination time of ds-MCE include esophageal transit time (ETT), gastric examination time (GET), gastric transit time (GTT), small bowel transit time (SBTT), and total running time (TRT). ETT is defined as the time between the first esophageal image and the first gastric image. GET is defined as the time for examination of whole stomach twice. GTT is defined as the time between the first gastric image and the first duodenal image. SBTT is defined as the time between the first duodenal image and the first cecal image. TRT is defined as the time of the last picture taken by the capsule. Capsule endoscopy completion rate (CECR) is also recorded which defined as the proportion of the capsule that has a complete visualization of the entire small bowel¹⁴. Examination time of EGD is defined as the duration from the endoscope entering to exiting from the esophagus.

12) Patient satisfaction score of ds-MCE and EGD procedures. After completing the ds-MCE procedure or EGD procedure, patients will undergo a face-to-face interview at which they are asked to respond to the questions on the three-item questionnaire that addressed procedure satisfaction.

a) Did you experience discomfort during the ds-MCE/EGD procedure?

4 = none; 3 = minor; 2 = mild; 1 = severe; 0 = intolerable

b) Did you experience discomfort after the ds-MCE/EGD procedure?

4 = none; 3 = minor; 2 = mild; 1 = severe; 0 = intolerable

c) How would you rate the entire ds-MCE/EGD examination procedure?

4 = very comfortable; 3 = comfortable; 2 = tolerable; 1 = uncomfortable; 0 = very uncomfortable

6.2 Safety outcomes

Safety outcomes in this study will be assessed based on adverse event reporting. All adverse events that occur during the course of the study will be diligently recorded and documented.

7. Statistical Considerations

7.1 Objective and Hypothesis

Objective

The primary aim of this study is to assess the accuracy of ds-MCE for detection of EGV in patients with liver cirrhosis.

Hypothesis

The primary objective of this study is to evaluate the diagnostic performance of ds-MCE in detecting EGV by assessing its sensitivity and specificity, using EGD as the reference standard. The hypothesis is that both the sensitivity and specificity of ds-MCE for detecting EGV will exceed 85% when compared to EGD. The target value of 85% was set based on literature review¹⁵ and expert consensus from the steering committee.

H_{01} : Sensitivity $\leq 85\%$

H_{11} : Sensitivity $> 85\%$

H_{02} : Specificity $\leq 85\%$

H_{12} : Specificity $> 85\%$

7.2 Statistical Analysis Set

The analyses will be performed on modified intent-to-treat (mITT), per protocol set

(PPS) and safety analysis set (SAS). Each analysis set will summarize the number of subjects and its percentage from subjects.

Efficacy set: The analysis of mITT is primary, and PPS is a sensitivity analysis of mITT.

The effectiveness analyses will be based on mITT population who go through procedures of ds-MCE and EGD modalities and can be evaluated for the results of EV and GV.

The effectiveness analyses will also be conducted on the PPS, which includes all subjects in the mITT population who have no major protocol deviations (defined to be protocol violations that may have a significant impact on subject outcomes) and who do not meet any of the following criteria:

- Subject withdraws
- Capsule ingestion failure
- Esophageal or gastric examination failure under ds-MCE
- Esophageal or gastric examination failure under EGD
- System technical failure of ds-MCE or EGD

Safety Set: The evaluation of safety parameters will be conducted on the SAS

SAS (Safety Analysis Set): actual data that has been inspected at least once and has safety indicators recorded. Security missing values do not need to be carried forward.

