7.3.3 Missing data

The primary analysis will be conducted on both mITT and PPS. For mITT analysis, the observed cases (OC) for each visit will be used and the worst outcome carried forward (WOCF) method will be applied for the primary endpoint to impute missing data, unless otherwise specified.

No imputation for missing data will be performed for the secondary and safety outcomes analysis.

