7.3.7 Efficacy Analysis

7.3.7.1 Analyses for Primary Outcome

The primary outcome is the diagnostic accuracy of ds-MCE for discrimination of patients with EGV using sensitivity and specificity, along with the corresponding 95% CIs estimated using the Wilson's method¹⁶. Sensitivity and specificity will be compared with 85% using one-sample exact test. The accuracy, and positive and negative predictive values (PPV and NPV) will be calculated as other measures simultaneously, along with the corresponding 95% CIs estimated using the Wilson's method.

- True Positive (a): Both ds-MCE diagnosis and EGD results determine the presence of esophageal or gastric varices, and the location (esophagus or stomach) is consistent.
- False Negative (c): ds-MCE diagnosis determines no cases of esophageal or gastric varices, while EGD results determine the presence of esophageal or gastric varices.
- True Negative (d): Both ds-MCE diagnosis and EGD results determine the absence of esophageal or gastric varices.
- False Positive (b₁): ds-MCE diagnosis and EGD results both determine the presence of esophageal or gastric varices, but the locations (esophagus or stomach) are inconsistent.
- False Positive (b₂): ds-MCE diagnosis determines the presence of esophageal or

gastric varices, while EGD results determine the absence of esophageal or gastric varices.

Table1. Four-grid table for ds-MCE and EGD assessment results

ds-MCE	EGD		Non-varices
	Varices	Inconsistent location in the stomach or esophagus	
Varices	a	b ₁	b ₂
Non-varices	c		d

$$\text{Sensitivity (SE)} = a/(a+b_1+c) \times 100\%$$

$$\text{Specificity (SP)} = d/(b_2+d) \times 100\%$$

$$\text{Accuracy} = (a+d)/(a+b_1+b_2+c+d) \times 100\%$$

$$\text{PPV} = a/(a+b_1+b_2) \times 100\%;$$

$$\text{NPV} = d/(c+d) \times 100\%;$$

Sensitivity Analyses for the Primary Outcome

No sensitivity analysis will be conducted for this study.

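### The mITT definition, the PPS list and the WOCF rule conflict over patients with an EGD result but no evaluable ds-MCE; whether this changes the sensitivity verdict is conditional

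*SAP*

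**What the plan says.** **Primary set.** SAP 7.2 and protocol 9.3 rest the effectiveness analyses on the "mITT population who go through procedures of ds-MCE and EGD modalities and can be evaluated for the results of EV and GV". On ranking they say: "The analysis of mITT is primary, and PPS is a sensitivity analysis of mITT".

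**PPS.** The same sections define PPS as a set "which includes all subjects in the mITT population who have no major protocol deviations" and who meet none of five listed criteria. One of the five is "Capsule ingestion failure". The others are withdrawal, examination failure under ds-MCE, examination failure under EGD, and technical failure.

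**Missing data.** SAP 7.3.3 and protocol 9.4.3 state: "The primary analysis will be conducted on both mITT and PPS". For mITT they use observed cases and add that the "worst outcome carried forward (WOCF) method will be applied for the primary endpoint to impute missing data".

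**Classification.** SAP 7.3.7.1 defines the cells of the 2x2 table, and each needs a ds-MCE diagnosis. The false-negative cell, for example, is: "ds-MCE diagnosis determines no cases of esophageal or gastric varices, while EGD results determine the presence of esophageal or gastric varices". The same section ends with: "No sensitivity analysis will be conducted for this study".

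**The concern.** The rules collide over one kind of patient: EGD gives a result, but ds-MCE was attempted without an evaluable reading. The mITT sentence leaves this patient out. The imputation rule and the capsule ingestion line make sense only if such a patient is in mITT. The 2x2 definitions do not help, because no cell takes a patient without a ds-MCE diagnosis. Worst outcome is not defined for a diagnostic classification, least of all when EGD is the missing result.

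The two treatments answer different questions: how accurate ds-MCE is when it yields a reading, or how accurate it is in everyone in whom it is attempted. The sensitivity test is planned at 90% against 85% with 80% power, so a few patients moved into the denominator could matter. This is a confirmatory test, and its primary table should not depend on which clause an analyst chooses to follow.

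**Working it through.** **1. Do the clauses fit the mITT definition?** Take mITT as evaluable for EV and GV on both procedures.
- WOCF for the primary endpoint: no mITT patient lacks a result, so the rule is empty.
- PPS line on capsule ingestion failure: a capsule that was not swallowed gives no ds-MCE reading, so no mITT patient can meet it.
- PPS lines on examination failure: not empty. Protocol 6.2.1.2 and 6.2.2 define procedural success as complete evaluation of esophagus and stomach. An incomplete examination that can still be evaluated may be in mITT and outside PPS.
- PPS called a sensitivity analysis in SAP 7.2, and none allowed in SAP 7.3.7.1: a direct contradiction.

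**2. Inputs** (SAP 5.3, 7.1, 7.3.1, 7.3.7.1). Null value 85%; assumed sensitivity 90% and specificity 94%; two-sided 5%; power 80%; EGV prevalence 62%; dropout 3%; N = 591; one-sample exact test; sensitivity = a/(a+b₁+c).

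**3. The plan's own figure.** For the exact test of 85% against 90% with upper tail 0.025, 356 EGV-positive patients give 80.8% power (success at 316 or more). Then 356/0.62 = 574.2. Inflating gives 574.2/0.97 = 592.0 or 574.2 × 1.03 = 591.4. The stated 591 is reproduced to within one patient, with dropouts outside the denominator.

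**4. Tipping point for sensitivity.** Expected EGV-positive patients: 591 × 0.62 = 366 with no loss, and 591 × 0.97 × 0.62 = 355 after 3% loss. I use 360 evaluable as a value in between. With x detected among n evaluable, score k unevaluable EGV-positive patients as misses and test x/(n+k) against 0.85:

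| Evaluable only | Last pass | First fail | k to fail |
|---|---|---|---|
| 320/360 (88.9%), p=0.039 | 320/360 | 320/361, p=0.055 | 1 |
| 324/360 (90.0%), p=0.006 | 324/365, p=0.047 | 324/366 (88.5%), p=0.067 | 6 |
| 333/360 (92.5%), p<0.001 | 333/375, p=0.043 | 333/376, p=0.060 | 16 |

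The p-values are two-sided exact; an upper tail of 0.025 gives the same verdicts. The bases 320/355 and 329/366 also tip at six. Over 354 to 367 EGV-positive patients with counts next to 90%, the range is 5 to 7.

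**5. Specificity.** The expected EGV-negative count is 591 × 0.97 × 0.38 = 218. At 205/218 (94.0%), ten added errors still pass (205/228, p=0.041) and eleven fail (205/229, p=0.063). Specificity has more margin.

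**6. How likely are six?** The documents give no ds-MCE failure rate, so any rate is an assumption. With 366 EGV-positive patients and a binomial count:
- 0% failures: none expected.
- 0.5%: 1.8 expected; chance of six or more about 1%.
- 1%: 3.7 expected; chance of six or more about 16%.

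**7. Predictive values.** SAP 7.3.7.1 takes NPV as d/(c+d). Suppose d = 205, and c = 36 from 324/360 with no location mismatches. NPV is 205/241 = 85.1%. Placing six failed examinations in cell c would give 205/247 = 83.0%, although none of the six had a negative reading. A counting rule for failures must therefore leave PPV and NPV alone.

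**The case against.** The strongest reply is that the primary set is already stated. The mITT sentence requires both procedures and evaluability. Protocol 5.4 calls consented patients who cannot be analysed per protocol drop-outs, and the sample size is inflated for a 3% loss. The imputation sentence speaks of observed cases at each visit, which suits a longitudinal trial better than one ds-MCE and one EGD, and it may be a carry-over. Most of this stands, and evaluable-only is the more natural reading.

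What does not fall away is that the only imputation rule for the primary endpoint is written for a set that has nothing missing. An analyst who took it seriously would produce a different table.

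Three stronger readings are tempting, but the documents do not support them.
- A reader might infer that the primary population is wholly open, or that most of the PPS list is void. Neither follows: the definition favours one reading, and only the capsule ingestion line is firmly impossible.
- A reader might infer that the sensitivity verdict is likely to be reversed. That needs a failure rate, which the documents do not give.
- A reader might infer a collapse in power. If failures count as errors and all 591 enter, joint power falls from 79% at no failures to 59%, 35% and 17% at 1%, 2% and 3%. Those figures rest on assumed rates, and on 90% and 94% holding only among evaluable patients. The documents do not say that they do; if those values already include failures, the loss disappears.

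The statement that the primary analysis is run on both sets is also weak evidence of conflict. It can mean that the primary outcome is analysed in both, with SAP 7.2 giving the ranking.

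**Conclusion.** The conflict is real and stands in the current text of both documents, except that the line excluding sensitivity analyses is in the SAP only. It is best described as a stated primary definition with clauses that cannot operate alongside it and a missing-data rule that points the other way.

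The size is conditional. Near an observed sensitivity of 90%, about six (5 to 7) unevaluable EGV-positive patients scored as misses turn a pass into a fail. The number is 1 at 320/360 and 16 at 333/360. This assumes that all of them are EGV-positive on EGD and that worst outcome means a miss. If there are no such patients, the two tables coincide. The subject disposition tables in SAP 7.3.5 would help to show how many patients are affected, but not which table is primary. It should be fixed, because the repair is small and the table concerned carries the confirmatory test.

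**What to change.** Before the 2x2 table is produced:

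1. Confirm one primary set in SAP 7.2 and protocol 9.3, chosen by the question the trial asks. If it is evaluable-only, keep the mITT sentence, delete capsule ingestion failure from the PPS list, and delete the observed-cases/WOCF sentence in SAP 7.3.3 and protocol 9.4.3. If it is all-attempted, redefine mITT as patients with an evaluable EGD in whom ds-MCE was attempted, and replace the WOCF sentence with the rule in item 2.
2. Report the other table alongside as a sensitivity analysis. In the all-attempted table, an unevaluable ds-MCE counts as an error in the sensitivity denominator if EGD shows EGV, and in the specificity denominator if it does not. Apply this to sensitivity, specificity and accuracy only; compute PPV and NPV from patients with a ds-MCE reading. Exclude patients without an evaluable EGD and list them with reasons.
3. Delete the SAP 7.3.7.1 sentence that rules out sensitivity analyses. State that the primary-outcome analysis is run on mITT as primary and on PPS as a sensitivity analysis.
4. If all-attempted is made primary, say in SAP 5.3 and protocol 9.2 whether the assumed 90% and 94% include failures. If they do not, restate the power over an assumed range of failure rates.

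The cost is wording in two documents and one extra table. Protocol 6.2.1.2 already records reasons for incomplete ds-MCE examinations on the CRF. The downside is that the all-attempted estimates will be less favourable if any examinations fail.

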7.3 Statistical Analyses

7.3.1 General Analysis Considerations and Convention

Descriptive statistics for continuous variables will include arithmetic mean (standard deviation) or median (interquartile ranges) as appropriate. Frequency and percentage will be calculated for categorical variables. Unless otherwise specified, for continuous variables, comparisons between groups will be assessed using the paired *t* test or Wilcoxon signed-rank test as appropriate. Categorical variables will be compared using the McNemar test as appropriate.

All statistical analyses will be performed using SAS version 9.4 (SAS Institute Inc, Cary, NC) and R version 4.2.2 (R Foundation for Statistical Computing). Unless otherwise specified, all significance testing will be 2-tailed using $\alpha = 0.05$. Tests will be declared statistically significant if the calculated p-value was <0.05 .

7.3.2 Interim Analyses

No interim analysis is planned for this study.

7.3.3 Missing data

The primary analysis will be conducted on both mITT and PPS. For mITT analysis, the observed cases (OC) for each visit will be used and the worst outcome carried forward (WOCF) method will be applied for the primary endpoint to impute missing data, unless otherwise specified.

No imputation for missing data will be performed for the secondary and safety outcomes analysis.

7.3.4 Multiple Comparisons

Since the primary outcome hypothesis testing based on the two primary endpoints should be met simultaneously, no multiplicity adjustment will be performed.

For the analysis of the secondary and safety outcomes, no adjustment for multiple comparisons will be made.

7.3.5 Subject Enrollment Status

(1) Subject Disposition

The disposition of all subjects will be summarized. Subject disposition tables will include the number (percent) of subjects who are:

Screened subjects and ineligible subjects;

Included in each analysis populations;

Discontinued from the study early, summarized by reasons for discontinuation.

(2) Subject Disposition by Study Site

Subject disposition by study site will be summarized by number of enrolled subjects, number (percent) of subjects who completed the study and who discontinued from the study early.

(3) Protocol Violations

Major protocol violations that led to the exclusion from PPS will be listed.

7.3.6 Demographics and Baseline Characteristics

All data recorded at baseline will be summarized and presented for each analysis set. Summary tables (descriptive statistics and/or frequency tables) will be provided for all

variables at different endpoints. For continuous variables, means and standard deviations will be presented, unless the variable has a skewed distribution, in which case medians, 25th and 75th percentiles will be presented. For categorical variables, the number and percentage of participants within each category will be presented. For each variable (continuous or categorical), the number of missing values will be reported.

Subjects' baseline characteristics include: Age (continuous), sex (male/ female), body-mass index (continuous), time since diagnosis of cirrhosis (continuous), etiology (hepatitis B virus infection/hepatitis C virus infection/alcoholic liver disease/ autoimmune hepatitis/primary biliary cirrhosis/non-alcoholic steatohepatitis /cryptogenic/other), Child-Pugh score (continuous), Child-Pugh Class (class A/class B/class C), decompensated cirrhosis (yes), indication for endoscopy (screening/ surveillance), clinical events (ascites/history of splenectomy/TIPS insertion/ history of endoscopic variceal therapy/ history of bleeding esophagogastric varices).

